APPENDIX 5. PROHIBITED CONCOMITANT MEDICATIONS

Refer to [Section 5.3.2](#) for more information on prohibited concomitant medications.

The following is a non-exhaustive list of medications that are prohibited because of their potential for metabolic interactions with tildacerfont. Most children in this study will not be taking the medications listed below. Any drugs of concern should be discussed with the MM.

alfentanil	darifenacin	itraconazole	paxlovid ^a	rivaroxaban
apixaban	diltiazem	ketoconazole	phenobarbital	sildenafil
atorvastatin	elagolix	lesinurad	phenytoin	simvastatin
avanafil	eletriptan	loperamide	posaconazole	St John's wort
avasimibe	ethinyl estradiol (>20 mcg)	lovastatin	pravastatin	teneligliptin
buspirone	felodipine	mibepradil	quetiapine	ticagrelor
carbamazepine	fluconazole	midazolam	repaglinide	triazolam
cenobamate	glyburide	nefazodone	rifampin	vardenafil
ciprofloxacin	isavuconazole	oseltamivir	rifapentine	voriconazole

^a Study drug should be held during paxlovid treatment but can be re-started 24 hours after last paxlovid dose.

Many oncology drugs and medications used to treat the hepatitis C virus and HIV are strong inhibitors of CYP3A4 but are not listed above simply because individuals with active cancer, hepatitis C, and/or HIV are excluded from this study.

APPENDIX 6. CLINICAL LABORATORY TESTS

Refer to [Section 7.1.5](#) for more information on clinical laboratory tests.

Laboratory Assessments	Parameters	
Hematology	Platelet count	
	RBC count	
	RBC indices: MCV, MCH, % reticulocytes	
	Hemoglobin	
	Hematocrit	
	WBC count	
	Differential: neutrophils, lymphocytes, monocytes, eosinophils, basophils	
Clinical Chemistry ¹	Potassium	ALP
	Calcium	ALT/SGPT
	Sodium	AST/SGOT
	BUN	GGT
	Creatinine	Total and direct bilirubin
	Total protein	Total bile acids
Coagulation	INR, PT, PTT	
Thyroid Panel	T3 (free and total), T4 (free and total), TSH	
Other Tests	Testosterone, ACTH, 17-OHP, A4, 11KT, and cortisol	
Routine Urinalysis	Specific gravity pH, glucose, protein, blood, ketones, bilirubin, urobilinogen, nitrite, by dipstick Microscopic examination (if blood or protein is abnormal)	

Abbreviations: 11KT=11-ketotestosterone; A4=androstenedione; ALP=alkaline phosphatase; ALT=alanine aminotransferase; AST=aspartate aminotransferase; BUN=blood urea nitrogen; GGT=gamma-glutamyl transferase; INR=international normalized ratio; MCH=mean corpuscular hemoglobin; MCV=mean corpuscular volume; PT=prothrombin time; PTT=partial thromboplastin time; RBC=red blood cell; SAE=serious adverse event; SGOT=serum glutamic-oxaloacetic transaminase; SGPT=serum glutamic-pyruvic transaminase; TSH=thyroid-stimulating hormone; WBC=white blood cell.

## LIST OF ABBREVIATIONS

---

Abbreviation	Description
11KT	11-ketotestosterone
17-OHP	17-hydroxyprogesterone
21-OHD	21-hydroxylase deficiency
A4	androstenedione
ACTH	adrenocorticotrophic hormone, corticotropin
ADL	activities of daily living
AE	adverse event
AESI	adverse event of special interest
ALP	alkaline phosphatase
ALT	alanine aminotransferase
AST	aspartate aminotransferase
BCRP	breast cancer resistance protein
BID	twice daily
BMI	body mass index
BSA	body surface area
CAH	congenital adrenal hyperplasia
CBC	complete blood count
CNS	central nervous system
CONSORT	Consolidated Standards of Reporting Trials
COVID-19	coronavirus disease 2019
CRF	corticotropin-releasing factor
CRF1, CRF2	corticotropin-releasing factor type-1 or type-2
CRO	contract research organization
C-SSRS	Columbia–Suicide Severity Rating Scale
CTCAE	Common Terminology Criteria for Adverse Events
CYP	cytochrome P450
DLT	dose-limiting toxicity
DMC	Data Monitoring Committee
EC	Ethics Committee
ECG	electrocardiogram
eCRF	electronic case report form
EDC	electronic data capture
eGFR	estimated glomerular filtration rate
EOS	end of study
EOT	end of treatment
ET	early termination

FDA	Food and Drug Administration
FOCP	female of childbearing potential
GC	glucocorticoid
GCP	Good Clinical Practice
GGT	gamma-glutamyl transferase
GI	gastrointestinal
GnRH	gonadotropin hormone-releasing hormone
HC	hydrocortisone
HIV	human immunodeficiency virus
HPA	hypothalamic-pituitary-adrenal
IB	Investigator's Brochure
ICF	informed consent form
ICH	International Council for Harmonisation of Technical Requirements for Pharmaceuticals for Human Use
INR	international normalized ratio
IRB	Institutional Review Board
IUD	intrauterine device
IUS	intrauterine system
MedDRA	Medical Dictionary for Regulatory Activities
MM	Medical Monitor
OTC	over the counter
PBPK	physiologically-based pharmacokinetic
PD	pharmacodynamic(s)
PK	pharmacokinetic(s)
PROMIS	Patient Reported Outcomes Measurement Information System
QD	once daily
QTcF	Fridericia-corrected QT interval
SAE	serious adverse event
SAP	Statistical Analysis Plan
SUSAR	suspected unexpected serious adverse reaction
SWYC	Survey of Well-being of Young Children
TART	testicular adrenal rest tumor
TEAE	treatment-emergent adverse event
ULN	upper limit of normal
v	version
WHO DD	World Health Organization Drug dictionary

## 1 REVISION HISTORY

Version	Date	Document Owner	Revision Summary
1.0	08JAN2023	[name]	First version (submitted)
1.1	05MAR2024	[name]	Corrected First version (submitted)
2.0	18APR2024	[name]	Revision

## 2 RELATED DOCUMENTS: PROTOCOL AND CASE REPORT FORMS

Version	Date
Protocol Version 1.0	04AUG2021
Protocol Version 2.0	27SEPT2021
Protocol Version 3.0	10MAR2022
Protocol Version 4.0	14OCT2022
Case Report Forms v7.0	21JAN2024
Protocol Version 5.0	30NOV2023

## 3 COMMITMENT TO GOOD STATISTICAL PRACTICE

### 3.1 Definition of Good Statistical Practice

The International Council for Harmonisation (ICH) Guideline on Statistical Principles for Clinical Trials (ICH E9) implicitly defines good statistical practice. Good statistical practice includes both appropriate statistical designs to minimize bias and maximize precision of analysis plus operational excellence to assure credibility of results. The scientific design associated with any clinical trial is found in the protocol. More detailed and pre-specified statistical analysis methods can be found in this statistical analysis plan.

We interpret the operational side of good statistical practice as a transparent, reproducible, and validated approach to acquiring and analyzing clinical trial data. Reproducible research depends upon process transparency and provides auditability of the statistical analysis. Analysis transparency requires that a navigable electronic process chain exists from defining the objective of the analysis to creating the results.

### 3.2 Use of Standards

Data standards are foundational for creating an environment where tools can be leveraged at different points in the analysis process. Data standards for clinical development of drugs have been defined and are maturing under various initiatives through the Clinical Data Interchange Standards Consortium (CDISC). Spruce Biosciences uses study data tabulation model (SDTM) data sets and Analysis Data Model (ADaM) statistical analysis files for producing analysis

results. Other applicable standards include regulatory guidance from the Food and Drug Administration (FDA) and ICH:

- ICH Guideline on the Structure and Content of Clinical Study Reports (ICH E3)
- ICH Guideline for Good Clinical Practice (ICH E6)

## 4 PURPOSE OF THE ANALYSIS PLAN

This statistical analysis plan (SAP) pre-specifies the statistical analysis methods for supporting the completion of a clinical study report (CSR) of Study SPR001-205 for tildacerfont, an investigational drug candidate designed to treat classic congenital adrenal hyperplasia (CAH). This SAP will be used to analyze the safety, efficacy, and pharmacodynamics (PD) data collected during the study. The planned analyses identified in this SAP may be included in regulatory submissions and/or future manuscripts.

The analysis methods described in this plan are considered *a priori*, in that they have been defined prior to clinical database lock. Exploratory analyses that are not defined in this SAP may be performed to support the clinical development program. Any post-hoc or unplanned analyses that are performed for the CSR, but not defined in this SAP, will be documented in the CSR. Changes from the planned analyses are described in [Section 15](#). Should the SAP and the protocol be inconsistent with respect to any further planned analyses, the language of the SAP is governing.

The analysis of pharmacokinetic (PK) concentration data and its parameters will be documented separately. The data analysis for the open label extension period will be covered in a separate SAP.

## 5 STUDY DESIGN

This is a Phase 2 open-label study with up to 10 cohorts that will evaluate the safety, efficacy, and PK of different tildacerfont dosing regimens potentially up to 200mg once daily (QD), in Cohorts 1-3, for 12 weeks in children with classic CAH, and up to 400mg BID, in Cohorts 4-9, for 4 weeks in children and adults with classic CAH.

Cohorts 1 and 1a (if indicated) in children aged 11-17 years, Cohort 2 in children aged 11-17 years, and Cohort 3 in children aged 2-10 years will study weight-based dose equivalents of up to 200mg QD. Treatment in Cohorts 1-3 will be for 12 weeks. Cohorts 4 and 5 in adults, Cohorts 6 and 8 in children aged 11-17 years, and Cohorts 7 and 9 in children aged 2-10 years will evaluate doses higher than 200mg QD that will be administered BID for 4 weeks.

Cohort 4 (adults) and Cohort 6 (11-17 years) will initiate concurrently at 200mg BID (200 mg BID has been previously evaluated in adults in study SPR001-201). Upon completion of the 4-week dosing on 4 sentinel subjects from Cohorts 4 and 6 combined, the DMC will assess safety data and provide recommendations on continued dosing. If the DMC assesses it to be safe to proceed to a higher dose, Cohort 5 (adults) may be initiated at 300mg or 400mg BID and Cohort 7 (2-10 years) may be initiated at 200mg BID. Following the completion of the 4-week

dosing periods for Cohorts 5 and 7, the DMC will review safety data from 4 sentinel subjects and offer recommendations on whether to proceed to Cohort 8 (11-17 years) and at what dose (300mg or 400mg BID). Following completion of the 4-week dosing period for 4 sentinel subjects in Cohort 8, the DMC will review the safety data and provide a recommendation on whether to proceed with Cohort 9 and at what dose (300mg or 400mg BID) ([Table 1](#)).

**Table 1** Study Cohorts

Cohort	Age	Sample Size	Corresponding Adult Dose	Treatment Duration
1	11-to 17-years	5	50 mg QD	12 Weeks
1a a	11-to 17-years	5	To be determined based on DMC recommendation (50 or 100 mg QD)	
2	11-to 17-years	5	200 mg QD	
3	2-to 10-years	10	50 mg QD, 100 mg QD, OR 200 mg QD	
4	>18-years	5	200 mg BID	4 weeks
5	>18-years	5+5 c	300 and/or 400 mg BID	
6	11- to 17-years	5	200 mg BID	
7	2- to 10-years	5	200 mg BID	
8 b	11- to 17-years	5+5 c	300 and/or 400 mg BID	
9	2- to 10-years	5+5 c	300 and/or 400 mg BID	
		Up to 70 subjects total		

Abbreviations: BID=twice daily; DMC=Data Monitoring Committee; QD=once daily.

a Cohort 1a is an optional interim dose cohort that may be enrolled only if needed per DMC recommendation and Sponsor decision, in the event of a safety concern in subjects in Cohort 1.

b Cohort 8 and 9 are adaptive cohorts that may be enrolled based on emerging safety data and per DMC and Sponsor recommendation/approval.

[figure not shown]
c +5 allows for the option of dosing 300mg before or after 400 mg Cohort is initiated if indicated by the DMC.

There are 7 scheduled visits over approximately 18 weeks for Cohorts 1 to 3; and 5 scheduled visits over approximately 10 weeks for Cohorts 4 to 9. Visits are detailed in [Table 8](#) and [Table 10](#). Any subject enrolled under protocol amendment 3 may be re-consented to protocol amendment 4

[figure not shown]
and receive the 12-week treatment course; however, because they will have already contributed PK data, they will not be required to have blood draws for tildacerfont concentration on Days 1 and 14 between 0.5 to- 1.5 hours and between 3 to 5 hours post dosing. Additionally, any subject enrolled under amendment 4 (or any other tildacerfont study) may be re-consented and enrolled under protocol amendment 5.

Clinical visits during the Treatment Period and Follow-up Period will include safety, efficacy, PK, and PD assessments. [Figure 1](#) and [Figure 2](#) depict study visits from Screening Period to Follow-up Period.

## Figure 1 Overall Study Design for Cohorts 1, 1a, 2, and 3

**Figure 2 Overall Study Design for Cohorts 4 through 9**

Assessments and procedures for evaluation of safety, efficacy, PK, and PD will be conducted per the protocol-specified schedule (see [Appendix A: Schedule of Events: Table 8, , Table 10 and Table 11](#)).

## 5.1 Randomization and Blinding

This study is an open-label trial with no randomization scheme.

## 5.2 Study Treatment

### 5.2.1 Study Drug Administration

Tildacerfont oral tablets will be provided in bottles of 25 mg, 50 mg and 200 mg. Subjects will take 1 to 6 tablets daily, depending on the dose and Cohort assignment. Cohorts 1 to 3 will receive doses QD. The dose will be taken with the evening meal. The first 2 weeks in Cohorts 1, 1a, and 2 will require dosing with a morning meal. Cohorts 4-9 will receive BID dosing. Each dose should be taken with the morning and evening meals. Day 1 and Day 14 morning doses of

tildacerfont will be administered in the clinic for Cohorts 1, 2, 4, 5, 6, 7, 8, and 9 (and 1a, if indicated) and Day 1 only administration of tildacerfont for Cohort 3 ([Table 13](#)).

The amount of study drug that a subject will receive will depend on the assigned dose, age, and body weight ([Table 13](#)); for subjects in Cohorts 4 to 9 the screening weight measurement will be used to determine the dose of study drug, subjects in Cohorts 1-3 dose will be adjusted as needed during each visit, and for all subjects continuing in the extension period of the study the most recent weight measurement will be used to calculate the dose of study drug.

### 5.2.2 *Glucocorticoid Replacement Therapy*

Subjects must be on a stable dose of glucocorticoid (GC) replacement therapy for at least 1 month before screening. Subjects with the salt-wasting form of CAH who take mineralocorticoids must also be on a stable dose of mineralocorticoid replacement for at least 1 month.

In all cohorts, GC dose (frequency, distribution of doses, or total daily dose) may be adjusted based on A4 levels at Weeks 4 (all subjects Cohorts 1 to 3; and subjects in Cohorts 4 to 9 if continuing in the extension) and 8 (all subjects in Cohorts 1 to 3), and Week 12 (subjects in Cohorts 1 to 3 if continuing in the extension period). In the extension, GC dose may be adjusted based on A4 levels at each visit (see [Table 9](#) and [Table 11](#) for schedule of events in extension cohorts).

The below A4-based algorithm will be used to guide changes to the GC replacement therapy ([Table 2](#)).

**Table 2 A4-Based Glucocorticoid Dose Adjustment Algorithm**

Androstenedione Levels	Change to GC Replacement Therapy
$A4 \leq \text{upper limit of normal (ULN)}$	Reduce GC Dose
$\text{ULN} < A4 \leq 1.5 \times \text{ULN}$	Maintain GC Dose
$A4 > 1.5 \times \text{ULN}$	Increase GC Dose

If change in GC therapy is warranted by the A4 algorithm, sites will contact subjects by telephone after the receipt of A4 results (within approximately 2 weeks) after each applicable study visit.

## 5.3 Assessments

[Appendix A: Schedule of Events: Table 8, Table 9, Table 10](#) and [Table 11](#) show the schedule of events for the study under Protocol v5.0.

### *5.3.1 Safety Assessments*

Safety will be assessed by repeated clinical evaluations including adverse events (AEs) (serious AEs [SAEs], AEs leading to discontinuation/withdrawal, dose limiting toxicities [DLTs], AEs of special interest [AESIs]); physical examinations; vital signs; electrocardiograms (ECGs); clinical laboratory tests (chemistry, hematology, coagulation [Screening only], thyroid panel, and urinalysis); and psychiatric evaluations for suicide risk (Columbia–Suicide Severity Rating Scale [C-SSRS], Patient Reported Outcomes Measurement Information System [PROMIS] Pediatric Short Form [SF] v2.0, the PROMIS Parent-Proxy SF v2.0, or the Survey of Well-Being of Young Children [SWYC]).

The Safety Population will be used for all safety analyses. Safety data will be listed by subject and summarized by adult equivalent dose levels (50, 100, 200 mg QD; and 200 mg, possibly 300 and/or 400 mg BID) using the frequency of event or descriptive statistical summaries, as appropriate. Listings and summary tables will be provided for AEs, clinical laboratory tests, vital signs, and ECG data. Urinalysis, psychiatric evaluations, concomitant medications ([Table 14](#)), and physical examinations will be presented in listings only.

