The adult exposure levels observed after 2 weeks of treatment were extrapolated to pediatric participants based on body weight and age for this study using a PBPK approach based on healthy adults. The PBPK model was based on *in vitro* and *in vivo* information on the metabolism and PK of tildacerfont and was validated using the plasma concentration-time profiles in healthy adults in the fed state. To account for differing CYP3A4 expression by age, the Upreti ontogeny profile was used in the pediatric dose predictions in three age groups, 2 to 5, 6 to 10, and 11 to 17 ([Upreti and Walhstrom 2016](#)). Pediatric doses on a mg/kg basis were predicted by age group to correspond to the adult exposures at the same dose levels. Within the lower dose cohorts (50 mg and 100 mg), dose bands were constructed such that participants would not receive a dose greater than 20% over the predicted mg/kg conversion. Weight bands were constructed such that participants in higher dose cohorts would not receive a dose greater than 10% over the predicted mg/kg conversion of the corresponding adult dose.

Preliminary PK data from Cohorts 1-3 show that the PBPK model overestimates drug exposure in children, such that the weight-based adult equivalent doses utilized in the children do not provide the exposures observed in adults. Additionally, an inverse relationship between age and exposure is apparent. This may be due to differences in drug metabolism across developmental stages, specifically CYP enzyme activity which is the primary driver of tildacerfont elimination. CYP enzyme activity peaks in early childhood and declines into adulthood. Consequently, children sometimes require relatively higher doses than adults to achieve optimal exposures of drugs that are eliminated by CYP-dependent metabolism (i.e., the Upreti ontogeny profile may not have adequately adjusted for physiologic differences that impact tildacerfont exposure).

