8.3.4.2. Adverse Event Data

AEs will be coded using the Medical Dictionary for Regulatory Activities (MedDRA). AE summaries will be presented by System Organ Class, Preferred Term, severity, and frequency and percentage of participants reporting each observed event.

AEs that occur before the first dose of study drug of the Treatment Period will be distinguished from TEAEs (defined in [Section 7.2.1](#)). All AEs, AESIs and TEAEs will be listed by participant. The frequency of participants who experience TEAEs will be summarized overall and by cohort. TEAEs will also be summarized by relationship to study drug and severity.

Listings will be provided for participants who experienced an SAE or discontinued study drug/withdrew from the study because of an AE.

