## 7 SAMPLE SIZE AND POWER

No formal sample size calculation was performed. A sample size of up to approximately 55 children (i.e., 30 children 11- to 17-years of age, and 25 children 2- to 10-years), will provide adequate data to assess the initial safety of tildacerfont in a pediatric population and provide data to support the continued use of the PBPK model to determine pediatric dosing requirements in future studies. Although this is a pediatric study, up to 15 adults are included in this study to allow for all new dosing regimens to be tested in adults prior to children. The safety profile of tildacerfont in adults will primarily be established in other studies.

The study is expected to enroll approximately 20 children across the first 3 cohorts (i.e., Cohorts 1, 2, and 3), 10 in the 11-to 17- year age group and 10 in the 2-to 10- year age group. If the optional Cohort 1a is initiated (up to 5 subjects), however, Cohorts 1 to 3 may enroll up to 25 children total, 15 in the 11-to 17-year-old age group and 10 in the 2-to 10-year-old age group. Up to an additional six cohorts (Cohorts 4-9) are planned to investigate BID dosing over 4 weeks of treatment. The study will also enroll up to approximately 15 adults aged  $\geq 18$  years across Cohorts 4 and 5; and up to approximately 30 children across 4 additional cohorts [up to 15 in the 11- to 17-year age group (Cohorts 6 and 8) and up to 15 in the 2- to 10-year age group (Cohorts 7 and 9)]. If all possible doses are studied, total sample size of this study may be up to approximately 55 children and 15 adults. Up to a total 70 subjects will be enrolled in the study. Please see [Table 1](#) for subject numbers by dosing cohort:

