## **14 SAFETY ANALYSIS**

The Safety Population will be assessed for AEs, SAEs, AEs leading to discontinuation/withdrawal, DLTs, AESIs, physical examination, vital signs, ECGs, and clinical laboratory tests. All analyses of the safety data will be performed by adult equivalent dose levels. Urinalysis, psychiatric evaluations, and concomitant medications will be presented in listings only.

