### **14.1 Adverse Events**

All AE verbatim terms reported on the eCRF will be coded using the Medical Dictionary for Regulatory Activities (MedDRA® version 24.1).

All reported AEs (including non-TEAEs) will be listed. Separate listings will be provided for SAEs, TEAEs leading to study drug discontinuation, DLTs, AESIs, and AEs related to COVID-19.

All TEAE counts will be by enrollment experience (re-enrollers will be counted once per enrollment) and not by event. Subjects reporting the same TEAE on multiple occasions will have, the highest severity (severe  $>$  moderate  $>$  mild) or study drug relationship (related  $>$  probable  $>$  possible  $>$  unlikely  $>$  unrelated) recorded for the event in each enrollment experience will be summarized. All AE summary tables will display the number and percentages of subjects per enrollment experience reporting TEAEs, unless otherwise specified.

An overall summary of AEs will be reported and will include the number and percentage of subjects experiencing any AEs, SAEs, TEAEs, TEAEs by maximum severity (highest toxicity grade), study drug related TEAEs by maximum severity (highest toxicity grade), study drug related SAEs, DLTs, AESIs, TEAEs leading to study drug discontinuation, and TEAEs leading to deaths.

The number and percentage of subjects experiencing each TEAE, study drug related TEAE, and SAEs will be displayed in summary tables by adult equivalent dose levels as well as by cohort according to system organ class and preferred term. Tables including only preferred term summarized by adult equivalent dose levels as well as by cohort for the number and percentage of subjects experiencing each TEAE will be presented.

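### The dose-level safety tables pool adults with children at every BID level, and if Cohort 8 or 9 uses both 300 and 400 mg BID, no stated summary table shows its children at a single dose

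*SAP*

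**What the plan says.** **Dose-level rule.** SAP 5.3.1 states: "Safety data will be listed by subject and summarized by adult equivalent dose levels". The levels it names are 50, 100 and 200 mg QD, and 200 and possibly 300 and/or 400 mg BID. SAP 14 is categorical: "All analyses of the safety data will be performed by adult equivalent dose levels". Protocol 8.3.4 uses the same grouping. None of the three mentions age.

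**By-cohort tables.** SAP 14.1 adds a second grouping for some tables. Those of TEAEs, drug-related TEAEs and SAEs are to be "displayed in summary tables by adult equivalent dose levels as well as by cohort according to system organ class and preferred term". A further TEAE table is described as "Tables including only preferred term summarized by adult equivalent dose levels as well as by cohort". Protocol 8.3.4.2 agrees on cohort: "The frequency of participants who experience TEAEs will be summarized overall and by cohort". Laboratory, vital-sign and ECG summaries are by cohort (SAP 14.2 to 14.4).

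**Overall AE summary.** SAP 14.1 also plans one summary table covering, among other items, maximum severity, DLTs, AESIs and TEAEs leading to study drug discontinuation. It states no by-cohort version, so the general rule of SAP 14 applies.

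**Exposure and purpose.** Protocol 1.2.3 reports, from preliminary data in Cohorts 1-3, that "the weight-based adult equivalent doses utilized in the children do not provide the exposures observed in adults". SAP 7 calls this a pediatric study, explains that adults are included so that new regimens are tested in them first, and adds: "The safety profile of tildacerfont in adults will primarily be established in other studies".

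**The concern.** The primary endpoint is safety, and SAP 7 makes children the population of interest. A table by adult-equivalent dose level puts adults and children in the same BID column. The protocol's own data say that a child on a nominally equivalent QD dose had lower exposure than an adult. An event confined to children is then diluted by adults, and an event concentrated in adults can be read as pediatric. A trend across the dose columns is also confounded with age, because the QD columns contain no adults and the BID columns do.

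The by-cohort tables are the natural remedy, since each cohort covers one age group. They work only while a cohort has one dose. Cohorts 5, 8 and 9 may each enroll a second group of 5 at the other of the two higher doses, and neither document asks for a split by dose within cohort.

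**Working it through.** **Inputs.** Cohort sizes and doses are from SAP Table 1 (the same as Protocol Table 1). Age by cohort is from Protocol 4.1.1.

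**Step 1: reproduce the planned maximum.** In the order 1, 1a, 2, 3, 4, 5, 6, 7, 8, 9: 5+5+5+10+5+10+5+5+10+10 = 70. By age:
- Adults (4, 5): 5+10 = 15.
- 11-17 years (1, 1a, 2, 6, 8): 5+5+5+5+10 = 30.
- 2-10 years (3, 7, 9): 10+5+10 = 25.

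This matches SAP 7: 55 children and 15 adults.

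**Step 2: who is in each dose-level column.**
- 50, 100 and 200 mg QD: Cohorts 1, 1a, 2 and 3 only, so 0% adults.
- 200 mg BID: Cohorts 4, 6 and 7, so 5 adults and 10 children; adult share 5/15 = 33%.
- 300 mg BID and 400 mg BID: Cohorts 5, 8 and 9 with 5 each per dose, so again 5/15 = 33% at each. If Cohort 9 does not open at that dose, 5/10 = 50%.

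**Step 3: who is in each cohort column.**
- Cohorts 6 and 7: children only, at 200 mg BID only.
- Cohort 8 or 9 with one dose: 5 children, all at that dose. The column isolates them.
- Cohort 8 or 9 with both doses: 10 children, 5 at 300 and 5 at 400 mg BID, in one column.

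**Step 4: combine.** In the two-dose case the cohort column mixes doses. The dose column mixes that cohort with the others treated at the same dose, including adults from Cohort 5 where they were enrolled at it. No stated summary table then shows that cohort's children at one dose; only the subject listings do. For the overall AE summary only the dose-level column is stated, so the pooling of Step 2 applies at 200 mg BID as well.

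**Step 5: what pooling does to a figure.** The documents give no event rates, so the counts below are assumptions for illustration. Intervals are two-sided 95% exact (Clopper-Pearson).
- Two events, both in children: pooled 2/15 = 13.3% (1.7% to 40.5%); children 2/10 = 20.0% (2.5% to 55.6%).
- Three of 10 children and no adults: 30% in children, pooled 3/15 = 20%.
- Two of 10 children and 3 of 5 adults: 20% in children, pooled 5/15 = 33%.
- No events, upper limit 1 − 0.025^(1/n): 21.8% for 0/15, 30.8% for 0/10, 52.2% for 0/5. The pooled column makes the evidence about children look tighter than it is.

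**The case against.** The best defense is that the plan already separates children from adults in its main AE tables. Those by system organ class and preferred term, and the table by preferred term alone, are also given by cohort, and cohorts are age-specific. That stands. At 200 mg BID any dilution in the dose column of those tables can be seen against the Cohort 6 and 7 columns, and the age split there would only repeat columns already planned.

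The second defense is that the gap at 300 and 400 mg BID is conditional. A second group of 5 is enrolled only if more than one dose is tested, on DMC recommendation. That also stands. A reader might infer that no AE table isolates children at 300 or 400 mg BID. The documents do not support this, because a Cohort 8 or 9 run at one dose is isolated by its own column.

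Third, tabulating by assigned nominal dose does not require equal exposure, and the exposure finding is preliminary and from QD dosing only. This is fair. A reader might infer that the dose conversion has been shown to fail at the BID doses, or that the SAP's grouping depends on it. The protocol gives no BID exposure result, and the SAP gives no such rationale. The finding is a reason not to read an all-ages column as if age did not matter, and nothing more.

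Fourth, subject-level listings cover all AEs, with separate ones for SAEs, DLTs, AESIs and TEAEs leading to discontinuation, and the mock shells are a separate document (SAP 9) that may already specify a split. The information is therefore not lost. But listings do not replace a summary of the primary endpoint in its target population, and the SAP text as written directs the pooled layout.

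**Conclusion.** The point holds in a limited form. The stated dose-level rule pools adults with children at each BID level, with 5 of 15 adult if all cohorts at that level enroll as planned, and leaves the QD levels all pediatric. The by-cohort tables repair this for TEAEs, related TEAEs and SAEs by term, except where Cohort 8 or 9 enrolls at both 300 and 400 mg BID and other cohorts are treated at the same doses. The overall AE summary is not repaired at any BID level where both adults and children enroll, so its counts for maximum severity, DLTs, AESIs and discontinuations have no stated pediatric version.

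This rests on the planned cohort sizes, on reading the overall summary as governed by SAP 14 because no other grouping is given, and on the shells not adding a split. The size of any distortion is unknown, since the event rates above are assumed. The change is worth making because it is cheap and lets the primary endpoint describe children at each dose. The present layout does not make the safety data unusable.

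**What to change.** In SAP 5.3.1, 14 and 14.1, state that the AE tables, including the overall summary and the DLT and AESI counts, are presented by dose level within age group: 2-10, 11-17, all under 18, and 18 years or older. This also shows dose within Cohorts 5, 8 and 9. Base the description of pediatric safety on the under-18 columns and keep the all-ages column as supportive. Align Protocol 8.3.4, or record the change in SAP 15, since Protocol 8.3.1 allows analysis changes to be specified in the SAP before database lock.

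The cost is SAP wording and extra table columns. Age is already collected, and SAP 11.3.1 already defines categories that collapse to these groups. The drawback is small cells, about 5 to 10 children per dose level, so the tables remain descriptive. The by-cohort tables already have cells of that size.
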